## 9 RESEARCH METHODS

### 9.1 Study Design

Multinational, multicenter, prospective, observational, non-interventional study

### 9.2 Setting

Approximately 8000 patients from different care settings (primary care and secondary care, different specialties) will be enrolled consecutively at a total of approximately 800 sites. It is estimated that each site will contribute 10 patients, although additional patients - subject to approval - may be considered. At each study site, the patients will be enrolled consecutively. Patients will be stratified for High and Very High Risk (per physicians' assessment) as well as for previously and newly treated patients. Sites will be required to complete a patient screening log of eligible patients for this disease registry at their treatment centers. This log will document

how patients came to be included or excluded from the study, in order to assess the representativeness of the study population. Minimal information will be recorded for all patients who are screened for study enrolment, but no patient-identifiable information should be recorded. Those patients who provide their informed consent will be enrolled into the study.

**Study population:**

The study population consists of Very High Risk and High Risk dyslipidemic patients previously diagnosed and treated as well as newly treated patients receiving their first LMT. At baseline data collection point, baseline characteristics (LDL-C and other lipid parameters, CV risk assessment, concomitant diseases such as diabetes and congestive heart failure, certain HEOR variables) and relevant medical history (CV events such as myocardial infarction and stroke) will be documented.

In addition, for the previously diagnosed and treated patients, details on the lipid modifying treatment during the year before enrolment will be collected.

This information will be collected from the patients' chart from all dyslipidemia-related visits at which the patient has been seen by the physician, starting from date of diagnosis.

At the follow-up data collection point at 1 year ( $\pm$  2 months), available information on the patients' routine management between baseline and this data collection point, and efficacy and safety variables will be collected: LDL-C and the other lipid parameters, inflammatory status, overall CV risk scores (SMART and Framingham risk scores will be calculated centrally based on collected patient information), CV events such as myocardial infarction and stroke, diabetes related parameters, renal function parameters, and the lipid-modifying therapy. As an optional assessment, PRO questionnaires will be completed by the patient preferably in the physician's office.

Electronic data capture (EDC) will be used for the recording of the information.

As this is a non-interventional study, only data that is based on routine clinical practice will be documented. Treatment pattern and treatment initiation, continuation or changes are solely at the discretion of the physician and the patient. There will be no attempt to influence the prescribing patterns of any individual treating physician. All medication will be prescribed according to usual standard of care and will not be provided by the study sponsor. Participation in the study will in no way influence payment or reimbursement for any treatment received by patients during the study.

### **Participating Centers**

Patients will be recruited from approximately 800 sites in Ireland, UK, Portugal, Spain, France, Belgium, the Netherlands, Denmark, Germany, Switzerland, Italy, and Austria, as well as Norway and/or Sweden and/or Finland. The sites may be office-based or hospital-based, and may be involved with either primary or specialized care, the latter including cardiology, diabetes, lipidology.

Different databases are used to put a site list of potential sites together (DSE internal database, local CRO databases, external databases as available). At least 3 times the targeted number of active sites are contacted by sending a site qualification questionnaire to be completed. These contacted sites are free to accept or refuse to participate in the NIS. A stepwise process for site selection will be performed to allow for representative regional distribution of sites and site specialties. Geographic representativeness within the country is maintained as sites are selected from each province and, where applicable, language region.

The site must meet the following criteria in order to be selected for participation in this study:

- To have access to patients on LMTs or suitable for LMTs

- To be able to document the data in the English language
- To be able to complete the study in the EDC system
- To be able to conduct the study adequately, with enough time and staff to identify eligible patients, conduct the patient consent process, participate in required trainings, enter study data, and follow-up with study related activities
- To agree in following-up patients for a period of 1 year per patient according to clinical routine.

### **Eligibility Criteria**

Very High Risk and High Risk dyslipidemic patients requiring LMT's are eligible for enrolment. Further inclusion criteria

- $\geq 18$  years of age
- not simultaneously participating in any interventional study
- providing written informed consent for participation in the study (ICF)
- life expectancy  $> 1$  year

Patients will be stratified for High and Very High Risk as well as for previously and newly treated patients.

As this is a non-interventional study, no explicit exclusion criteria are defined.

### **Patient Groups**

There are no formal patient groups planned. No comparator groups will be introduced.

### **Schedule**

The total study period from FPI to LPO is 30 months. The individual start per country depends on the approval status of the protocol by the responsible Ethics Committee and Competent Authorities and will range approximately from Q3 2019 to Q4 2020. Per country, the patient recruitment period consists of 9 months, followed by a 12-month follow-up period per patient. It is expected that the last patient will complete the study in Q4/2021. The final study report is expected to be available in Q4/2022.

Patients eligible for the study at the site will be documented in a screening log to allow for judgement on representativeness of patient inclusion.

Patient data will be documented at two data collection points in time:

- Baseline at enrolment,
- FU1 approximately  $12 \pm 2$  months after baseline (face-to-face meeting preferred)

At baseline, the patients' medical history will be documented as well as the currently applied therapy. At the annual follow-up data collection point, changes in therapy and disease status since the last data collection point will be documented. At the baseline and the follow up data collection point the patients will be asked to complete the patient reported outcome (PRO) questionnaire EQ-5D-5L and the PAM-13 questionnaire.

### 9.3 Variables

#### Parameters recorded during the observation period:

*To be documented at baseline (if available):*

- Eligibility
- Demographic and sociodemographic variables
- Vital signs
- Medical history, including CVD risk status-related medical history:
  - CV risk assessment with or without utilization of risk score
  - history/diagnosis and current status of dyslipidemia
  - heterozygous familial hypercholesterolemia (HeFH)
  - documented ASCVD either clinical or unequivocal on imaging
- Concomitant diseases
- For diabetic patients
  - disease type and date of diagnosis
  - treatment
  - microvascular complications
- Current concomitant medication for CVD
- Previous / current dietary restrictions
- Previous / current use of lipid-modifying treatment
 

Previous / current use of lipid-modifying treatment including details of dose, dose modification, switching, combination therapy, drug intolerance, insufficient responsiveness, investigators and patients assessment on compliance

  - Statin(s)
  - Bile acid sequestrant(s)
  - Cholesterol absorption inhibitor (Ezetimibe)
  - PCSK9 inhibitor(s)
  - Nicotinic acid
  - Drug combinations
  - Bempedoic acid and/or bempedoic acid fixed dose combination with ezetimibe
  - Other
- Laboratory parameters
  - Lipid variables
    - LDL-C
    - HDL-C, non-HDL-C, TC, apoB, TG, Lp(a)
  - Diabetes-related parameters
    - fasting glucose
    - HbA1c
  - Inflammatory status
    - hsCRP
  - Renal function parameters (GFR, serum creatinine, blood urea nitrogen (BUN))
  - Other laboratory parameters (liver function, serum chemistry, hematology)
- HEOR parameters
  - Hospital admissions
  - Length of hospital stay
  - Number of days in ICU
  - Interventions
  - Other HEOR parameters

- Adherence to former and current treatment
- Patient reported outcomes (EQ-5D-5L, PAM-13)

*To be documented at 1-year follow-up (if available):*

- Vital signs
- CVD risk status:
  - CV risk assessment with or without utilization of risk score
  - history/diagnosis and current status of dyslipidemia
  - heterozygous familial hypercholesterolemia (HeFH)
  - documented ASCVD either clinical or unequivocal on imaging
- Concomitant diseases
- For diabetic patients
  - disease type and date of diagnosis
  - treatment
  - microvascular complications
- Current concomitant medication for CVD
- Previous / current dietary restrictions
- Previous / current use of lipid-modifying treatment
 

Previous / current use of lipid-modifying treatment including details of dose, dose modification, switching, combination therapy, drug intolerance, insufficient responsiveness, investigators and patients assessment on compliance

  - Statin(s)
  - Bile acid sequestrant(s)
  - Cholesterol absorption inhibitor (Ezetimibe)
  - PCSK9 inhibitor(s)
  - Nicotinic acid
  - Drug combinations
  - Bempedoic acid and/or bempedoic acid fixed dose combination with ezetimibe
  - Other
- Clinical events associated with the lipid modifying treatment modalities:
  - Insufficient lipid lowering efficacy
  - Muscle-associated symptoms
  - New-onset diabetes mellitus
  - Reduced kidney function
  - Drug-drug interaction
  - Noncompliance
  - Neurocognitive impairment
  - Laboratory abnormalities
  - Other
- Adverse drug reactions associated with the use of bempedoic acid and/or bempedoic acid fixed dose combination with ezetimibe
- Laboratory parameters
  - Lipid variables
    - LDL-C
    - HDL-C, non-HDL-C, TC, apoB, TG, Lp(a)
  - Diabetes-related parameters
    - fasting glucose

- HbA1c
- Inflammatory status
  - hsCRP
- Renal function parameters (GFR, serum creatinine, blood urea nitrogen (BUN))
- Other laboratory parameters (liver function, serum chemistry, hematology)
- HEOR parameters
  - Hospital admissions
  - Length of hospital stay
  - Number of days in ICU
  - Interventions
  - Other HEOR parameters (e.g. insurance status, employment status, education)
  - Adherence to former and current treatment
  - Patient reported outcomes (EQ-5D-5L, PAM-13)\*

\*For documenting PRO (Patient Reported Outcomes) two validated questionnaires/assessments will be used as explained below.

**EQ-5D-5L.** The EuroQol (EQ-5D-5L), developed by the EuroQoL group, is a generic utility measure rating the current overall health states. It consists of five domains (mobility, self-care, usual activities, pain or discomfort, and anxiety or depression) and a visual analogue scale (VAS). The scores range from 0 to 100 based on the level of health for each domain given by participants. A score of 100 indicates that the current health is equivalent to full health; a score of 0 indicates that the current health is equivalent to death. According to the scores of the five domains, a sum utility score is calculated ranging from 0 to 1. A score of 1 represents a perfect state. In addition, patients have to rate their current health on a 20-centimeter vertical visual analogue scale scored from 0 to 100 reflecting the continuum from a best imaginable to the worst imaginable health state. The EQ-5D is proved to be a reliable, valid, self-reported measure. It is used most widely for general healthcare evaluation, including cost-utility evaluation.

**PAM-13.** PAM assesses patient knowledge, skills, and confidence for self-management based on 13 items.

It segments individuals into one of four activation levels along an empirically derived 100-point scale.

Each level provides insight into an extensive array of health-related characteristics, including attitudes, motivators, and behaviors. Individuals in the lowest activation level do not yet understand the importance of their role in managing their own health, and have significant knowledge gaps and limited self-management skills. Individuals in the highest activation level are proactive with their health, have developed strong self-management skills, and are resilient in times of stress or change.

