### 8.2 Secondary Objectives

The secondary effectiveness objectives are to document:

- The relationship between the above-mentioned treatment modalities and plasma levels of other potentially ASCVD-modifying cholesterol fragments, namely HDL-C, non-HDL-C, TC, apoB, TGs, and Lp(a).
- Changes in the inflammatory marker hsCRP over time  
Changes in the patient's overall CV risk assessment over time measured through CV risk score calculators

The secondary safety objectives are to document:

- Clinical events associated with the various treatment modalities:
  - Laboratory abnormalities
  - Muscle-associated symptoms
  - New onset and/or worsening diabetes
  - Changes in the patients' glycemic status over time
  - Adverse Drug Reactions associated with bempedoic acid and/or fixed dose combination with ezetimibe

Additional secondary objectives are to document:

- The characteristics of the sites and physicians caring for Very High Risk and High Risk patients
- The patients' use of lipid-modifying treatment, especially with regard to a switch from one drug class to another, a dose modification of a given drug, a switch from one statin to another, any evidence of statin intolerance or insufficient responsiveness to a statin, including a maximally tolerated statin, and any use of combination drug therapy
- Various HEOR parameters associated with the management of dyslipidemic patients, such as PRO and healthcare resource use.

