**Table 1: Data Collection Flow Chart**

Variable	Baseline	Follow-up
Eligibility criteria	x	
Baseline Characteristics	x	
Vital signs	x	x
Medical History	x	
Hypercholesterolemia risk factors and predisposing comorbidities	x	x
Use pattern of previous/current lipid modifying treatment	x	x
Previous and current dietary restrictions	x	x
Concomitant medications for cardiovascular disease	x	x
Concomitant diseases For diabetic patients: Disease type and date of diagnosis, detailed treatment information, microvascular complications	x	x
Laboratory examinations (as available in medical records*) *physicians will not be required to perform any mandatory laboratory assessment for this study	x	x
Clinical events and hospitalizations		x
Management of hypercholesterolemia and physician contacts	x	x
PRO	x	x
Resource consumption/Health care utilization	x	x
ADRs related to bemedoic acid and/or bemedoic acid fixed-dose combination with ezetimibe**		x

\*\* Only applicable for Patients with bemedoic acid and/or bemedoic acid fixed dose combination with ezetimibe treatment:

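### Muscle symptoms and new diabetes are listed at follow-up only as events associated with lipid therapy, worsening diabetes has no item or derivation rule, and muscle symptoms have no baseline item

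*Combined protocol and SAP*

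**What the plan says.** Section 8.2 (and the Summary) sets secondary safety objectives under the phrase "Clinical events associated with the various treatment modalities". They include muscle-associated symptoms, "New onset and/or worsening diabetes" and, as a separate item, "Changes in the patients' glycemic status over time".

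Section 9.3 lists what is collected. At follow-up, a list headed "Clinical events associated with the lipid modifying treatment modalities" contains "Muscle-associated symptoms" and "New-onset diabetes mellitus", together with items such as noncompliance, insufficient efficacy and a general 'other' entry. Worsening diabetes is not on it. The baseline list has no muscle-symptom item; the nearest entry is drug intolerance, recorded within the lipid-therapy history.

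Table 1 marks "Clinical events and hospitalizations" at follow-up only. It marks laboratory results at both time points, and likewise concomitant diseases with, for diabetic patients, "Disease type and date of diagnosis, detailed treatment information, microvascular complications". Section 9.3 lists fasting glucose and HbA1c at both. Everything is recorded only if available, and Section 9.4 states that no test is mandated.

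**The concern.** The checklist mixes two questions: did the event happen, and does the physician connect it with lipid therapy? If a site enters only events it connects with the drug, the count measures attribution as well as occurrence. The plan itself shows where expectation lies. Section 7 names muscle pain as the reason most often given for stopping statins, and the Summary says that some lipid-lowering drugs may raise the incidence of diabetes. The same muscle complaint could therefore be entered more readily under a statin than under another class, and frequencies by treatment modality would partly return what physicians already believed.

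Two further gaps follow. Section 9.2 enrols previously treated as well as newly treated patients, so some may already have muscle symptoms at enrolment; without a baseline item these are hard to separate from symptoms that arise later. Worsening diabetes, a named objective, has neither an item nor a rule saying which marker must change and by how much.

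**Working it through.** The plan states no figure on this point, and no arithmetic applies beyond a simple identity. The check compares the objective with the fields, outcome by outcome.

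1. **New-onset diabetes.** Objective: named in Section 8.2. Event item: present at follow-up, under the therapy-linked heading. Other fields, at both time points and outside that heading: concomitant diseases, diabetes type, date of diagnosis, diabetes treatment, fasting glucose, HbA1c. Section 9.2.4 adds that changes in disease status are documented at follow-up. A patient with no diabetes at baseline and a diagnosis dated after enrolment can be identified without the checklist. Result: measurable, but the text does not say which source will be used or that the denominator is patients free of diabetes at baseline.

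2. **Worsening diabetes.** Objective: named. Event item: none, apart from the 'other' entry. Other fields: HbA1c, fasting glucose, diabetes treatment and microvascular complications at both time points. Result: derivable, but with no definition. A derivation from laboratory values needs a pair from routine care, and the number of patients with one is unknown in advance.

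3. **Muscle-associated symptoms.** Objective: named. Event item: follow-up only, under the therapy-linked heading. Baseline: drug intolerance only, which records a consequence for treatment and not whether symptoms are present at enrolment. Other routes: Sections 9.4 and 11 send adverse drug reactions to spontaneous reporting outside the study, except for bempedoic acid products. For the other classes the checklist is therefore the only named muscle-symptom field. Result: occurrence cannot be separated from attribution, nor reliably new from ongoing.

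4. **How attribution enters a comparison.** For drug class k, let r_k be the true event frequency and a_k the probability that an event, once it has occurred, is entered as associated with therapy. The checklist frequency is r_k × a_k. The ratio of two classes is (r_1 / r_2) × (a_1 / a_2). With no true difference (r_1 = r_2), it equals a_1 / a_2. It is unbiased only if attribution is equal across classes. The documents give no value for any a_k, so the size of the bias cannot be calculated.

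5. **Whether the analysis removes it.** Section 9.7 plans subgroup comparisons of one-year changes and Cox models, with adjustment for age, sex and country. None of these covariates represents attribution by drug class, so adjustment would not remove the factor a_1 / a_2 from an analysis of checklist events by modality.

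**The case against.** The strongest reply has four parts.

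First, the checklist heading repeats the objective's own framing, so form and objective agree. That is true, and this is not a contradiction in the plan. But an association with a modality is better learned by comparing recorded events than by filtering at entry, so the shared wording does not remove the problem.

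Second, it is not established that sites will enter only drug-blamed events. The same list contains noncompliance and insufficient efficacy, which are not adverse effects; Table 1 labels its row without reference to treatment; and the eCRF wording is not in the documents. This stands, and it is why the bias is stated as possible and of unknown size.

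Third, prior and new muscle symptoms are not wholly indistinguishable. Drug intolerance is taken at baseline, Section 7 links statin intolerance chiefly to muscle effects, and Section 9.9 asks at follow-up for changes and events since the previous time point. This helps, but it does not identify a patient who has symptoms at enrolment and stays on treatment.

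Fourth, Section 9.7 leaves detailed methods to a SAP finalised by database lock, and that text is not in the documents. Definitions for diabetes could appear there. A SAP cannot, however, recover muscle data that were never collected.

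A reader might infer that diabetes is collected only at follow-up as a therapy-linked event and so cannot be measured. The documents do not support this: the diabetes and glycaemic fields are listed at both time points outside the checklist. A reader might also infer that new-onset diabetes will be reported over the whole analysis set. Section 9.7 describes general summaries but allows selection of patients by variable, so that denominator is not shown to be planned.

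**Conclusion.** The point holds as a gap in definition and recording. For diabetes, the data are planned and what is missing is a derivation rule, an at-risk group and a statement on missing pairs. For muscle symptoms, the gap is in collection: one follow-up item tied to therapy and no baseline counterpart. Checklist frequencies, if reported by modality as they stand, would be open to differential attribution, and for muscle symptoms also to mixing ongoing with new complaints.

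The size is unknown. Multiplying an assumed incidence, diabetic share and attribution rate would give an apparent under-count, but none of those inputs is in the documents. The product would also apply only if the checklist were the sole source and the whole analysis set the denominator; the first is contradicted for diabetes and the second is not stated. The conclusion rests on two assumptions: that sites read the heading literally at least in part, and that no SAP text supplies the missing rules. The study is exploratory and has no primary endpoint, so this affects the reading of the secondary safety results and not the primary objective.

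**What to change.** 1. In the SAP, derive new-onset diabetes from concomitant disease status, date of diagnosis, diabetes treatment, fasting glucose and HbA1c, and report it among patients without diabetes at baseline. Derive worsening diabetes among patients with diabetes at baseline from pre-specified changes in HbA1c, fasting glucose, diabetes treatment or microvascular complications. Report the number of patients with paired values beside each result and state how missing pairs are handled. This needs wording only, and Section 9.7 allows the SAP to be finalised up to database lock.

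2. At follow-up, record muscle symptoms and new diabetes irrespective of suspected relation to treatment, and put the physician's attribution in a separate field. Report both counts.

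3. Where still feasible, add a baseline yes/no for current muscle symptoms, so that new and ongoing symptoms can be reported separately.

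The cost is one or two extra eCRF fields and a little site entry. The baseline field would be missing for patients already enrolled; on the stated milestones (first patient Q1/2020, last patient Q4/2020) that could be a large share by the date of this version, 26 August 2020. For those patients, the baseline drug-intolerance entry is the only substitute, and its limits should be stated in the report.
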